Section 5.1 Patient Eligibility Confirmation/ Inclusion Criteria	Administrative Change: Inclusion Criteria #2 shall read that a positive COVID-19 test is required within 7 days of randomization, either original diagnosis or a confirmation test. Administrative Change: Patient shall meet inclusion criteria #3 if the require ≥ 2L oxygen in order to normalize SaO2. An adequate SaO2 does not need to be maintained for the patient to qualify Revision: Inclusion criteria #6 was revised to read that a patient meets eligibility in the absence of any active or recurring clinically significant hepatic disease' and with a Albumin level of ≥2.5 g/dL
Section 8.1 Study Procedures/ Preventing Missing Data	Language Added: Patient follow-up should continue after discharge via approaches available to the site staff (e.g., telehealth visits, COVID-19 outpatient clinic, telephone calls, texts, and emails to the patient and close contacts). These efforts should prevent missing data while limiting additional public health risks and unnecessary community exposure.

- Number of days from randomization to the first day on which the subject satisfies one of the following three categories from the ordinal NIAID 8- point Clinical Progression Outcomes scale collected daily from randomization through Day 28:
 - Hospitalized, not requiring supplemental oxygen - no longer requires ongoing medical care;
 - Not hospitalized, limitation on activities and/or requiring home oxygen;
 - *Not hospitalized, no limitations on activities.*

To compare changes in clinical status of patients enrolled to CX-4945 treatment arm as compared to the control arm at Day 14 and Day 28.

- Difference in percentage of subjects with clinical recovery compared at Day 14 and Day 28. Clinical recovery is defined as:
 - Discharge from the hospital, or alleviation of cough (defined as mild or absent in a patient reported scale of 0=absent, 1=mild, 2=moderate, and 3=severe). Improvement must be sustained for at least 48 hours.
 - normalization of fever (defined as $<36.6^{\circ}$ C from axillary site, or $<37.2^{\circ}$ C from oral site or $<37.8^{\circ}$ C from rectal or tympanic site), normalization of respiratory rate (<24 bpm while breathing room air), resolution of hypoxia (defined as SpO2 \ge 93% in room air or P/F \ge 300

CONFIDENTIAL Page 10 of 66

mmHg). All these improvements must be sustained for at least 48 hours. Percentage of Participants at Each Clinical Status at Day 14 and Day 28 assessed by using the ordinal NIAID 8- point Clinical Progression Outcomes scale: 1) Death; 2) Hospitalized, on invasive mechanical ventilation extracorporeal membrane oxygenation *(ECMO)*; 3) Hospitalized, on non-invasive ventilation or high flow oxygen devices; 4) Hospitalized, requiring supplemental oxygen; 5) Hospitalized, not requiring supplemental oxygen - requiring ongoing medical care (COVID-19 related or otherwise); 6) Hospitalized, not requiring supplemental oxygen - no longer requires ongoing medical care; 7) Not hospitalized, limitation on activities and/or requiring home oxygen; 8) Not hospitalized, no limitations on activities To evaluate preliminary Difference in proportions of patients with evidence of anti-viral conversion of positive RT-PCR to negative RTactivity of CX-4945 as PCR as assessed at Day 1, Day 8, Day 14 and Day compared to the control 28. arm. Changes in chest imaging from Screening to Day 5 or 14 (if applicable) as defined by: Number of quadrants/ pulmonary lobes affected Change in number and/or size of COVID-19 pulmonary lesions (ground-glass opacity, consolidation, mix pattern) assessed by chest CT/X-ray

CONFIDENTIAL Page 11 of 66

[figure not shown]
	To evaluate the Clinical Benefit of Silmitasertib (CX-4945) relative to the control arm in patients with Severe COVID-19.	 Days of hospitalization from randomization through Day 28. Days of supplemental oxygen (if applicable) from randomization through Day 28. All-cause mortality status - the number of deaths occurred in each treatment group from randomization through Day 60. Days of non-invasive ventilation/high flow oxygen (if applicable) from randomization through Day 28. Days of invasive mechanical ventilation/ECMO (if applicable) from randomization through Day 28. Number of patients returned to room air after randomization through Day 14 or Day 28. Change in pulse oxygen saturation (SpO2) from randomization to Day 4, 8, 11, 14 and 28. Number of documented venous thromboembolism (VTE), arterial thrombosis (stroke, myocardial infarction, other) and microthrombosis events from randomization through Day 28. Changes in EQ-D5-5L (used as an indicator of symptom improvement) from randomization to Day 8, 14 and 28.
	To evaluate changes in inflammatory markers	 Changes in plasma IL-6 level from randomization to Day 4, 8, 11, and 14. Changes in CRP, LDH, CPK, ferritin, D-dimer from randomization to Day 4, 8, 11, and 14.
Ctude	This study will sensil	
Study Population:	_	e and non-pregnant female patients ≥ 18 years of age with use 2019 (COVID-19). Approximately 40 patients will be reatment groups.
Phase:	II	

CONFIDENTIAL Page 12 of 66

Description of Sites Enrolling Participants:	All patients will be enrolled at University of Arizona at Banner University Medical Center located in Phoenix or at University of Arizona College of Medicine in Tucson.
Description of Study Intervention:	CX-4945 will be administered twice a day for up to 14 days. The starting dose will be 1000 mg BID (2000 mg total daily dose).
Study Duration:	6 months (from study initiation until completion of data analyses)
Participant Duration:	The total duration of the treatment will be 14 days. Patients will be followed up at 28, 45 and 60 days from the start of the treatment. The total duration for each patient in the study (including screening) will be up to 67 days.

CONFIDENTIAL Page 13 of 66

1.2. SCHEMA

CONFIDENTIAL Page 14 of 66

1.3. SCHEDULE OF ACTIVITIES (SOA)

Table 1. Schedule of activities

Procedure/Assessments	Screeni ng Visit	Treatment Phase [16]					Follow-Up ^[17]		
Day	SV	Day 1 (Baseline)	Day 4	Day 8	Day 11	Day 14	Day 28	Day 45	Day 60
Window Period	Day -7 to Day -1	within 7 days after SV	±1 day	±1 day	±1 day	±1 day	±3 days	±3 days	±3 days
Informed Consent [1]	X								
Eligibility Evaluation [2]	X								
Subject Demographics	X								
Medical History [3]	X								
Physical Examination	X	X ^[4]		X ^[4]		X ^[4]	X ^[4]	X ^[4]	
Vital Signs ^[5]	X	X	X	X	X	X	X	X	
Assessment of clinical recovery [6]		X	X	X	X	X	X	X	
EQ-D5-5L		X		X		X	X		
Clinical Status - Ordinal 8-point Scale Assessment [7]	X	Daily from	X Daily from Day 1 through Day 28					X	X
Pulse oxygen saturation (SpO2)	X	X	X	X	X	X	X	X	
12-lead ECG	X					X			
Laboratory tests:									
Complete Blood Count [8]	X	X	X	X	X	X	X	X	
Biochemistry ^[9]	X	X	X	X	X	X	X	X	
Coagulation Indices [10]	X	X	X	X	X	X	X	X	
Serum/Urine Pregnancy Test	X					X			
Urinalysis ^[12]	X	X	X	X	X	X	X	X	
IL-6 levels		X	X	X	X	X			
PT-PCR ^[13]	X ^[13]	X		X		X	X		
Chest radiograph or CT	X	Day 5, Day 14 if indicated [14]							
Randomization [15]		X							
IP Administration (Treatment Arm A only)		Arm A: CX-4945 1000 mg BID PO on Days 1 - 14							

CONFIDENTIAL Page 15 of 66

Date: 01 February 2020

Mortality Status		X	X	X	X	X	X	X	X
Concomitant Medications	X	X	X	X	X	X	X		
Adverse Events		X	X	X	X	X	X	X	X

- [1] Informed consent must be obtained prior to patient participation in any protocol-related activities that are not part of routine care.
- [2] Initial evaluation of patient eligibility will be performed by Investigator.
- [3] Medical history and current therapies (medications and non-medications).
- [4] Symptom-directed physical examination
- [5] Vital signs will include blood pressure, heart rate, respiration rate, and temperature.
- [6] Based on hospital discharge or normalization of fever, respiratory rate, alleviation of cough, and resolution of hypoxia.
- [7] Clinical Assessment to be performed daily for at least 28 days, regardless of discharged or treatment discontinuation. Remote data collection methods, such as electronic data collection, phone, and telehealth assessments can be used from the day of discharge through Day 28, and at every follow-up visit (Days 28, 45 and 60).
- [8] Hemoglobin, Hematocrit (HCT), Red Blood Cells (RBC), White Blood Cells (WBC) with total and differential count, Absolute Neutrophil Count (ANC) and platelets.
- [9] Biochemistry (Comprehensive Metabolic Panel (CMP))
 - Hepatic function indicators: total bilirubin, alkaline phosphatase (ALP), aspartate aminotransferase (AST), alanine aminotransferase (ALT), total protein, albumin, lactate dehydrogenase (LDH)
 - Renal function indicators: BUN, Serum creatinine, creatinine clearance, or eGFR
 - Electrolytes: sodium, potassium, chloride, calcium and bicarbonate
 - Other: Creatine phosphokinase (CPK), C-reactive protein (CRP), serum ferritin, d-dimer
- [10] Prothrombin time (PT) and International Normalized Ratio (INR)
- [11] ONLY performed on women of childbearing potential.
- [12] Urine samples will be tested for color, appearance, specific gravity, pH, protein, glucose, occult blood, ketones, leukocyte esterase, nitrite, bilirubin, urobilinogen, and microscopic examination of urine sediment.
- [13] Positive standard RT-PCR assay or equivalent testing completed within 7 days prior to Day 1 is acceptable for eligibility evaluation at screening.
- [14] Chest radiograph or CT will be performed if clinically indicated by the treating physician
- [15] **Randomization:** Patient number and treatment arm allocation is performed on Day 1, prior to any Day 1 study assessments
- [16] Patient follow-up should continue after discharge via approaches available to the site staff (e.g., telehealth visits, COVID-19 outpatient clinic, telephone calls, texts, and emails to the patient and close contacts).
- [17] Follow-up visits may be performed via phone or telehealth, as appropriate

CONFIDENTIAL Page 16 of 66

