	Hospitalized, on invasive mechanical ventilation or acorporeal membrane oxygenation (ECMO);
· · · · · · · · · · · · · · · · · · ·	Hospitalized, on non-invasive ventilation or high flow gen devices;
4) H	Hospitalized, requiring supplemental oxygen;
	Hospitalized, not requiring supplemental oxygen - requiring oing medical care (COVID-19 related or otherwise);
· ·	Hospitalized, not requiring supplemental oxygen - no longer uires ongoing medical care;
	Not hospitalized, limitation on activities and/or requiring ne oxygen;
8) N	ot hospitalized, no limitations on activities
evidence of anti-viral activity of CX-4945 as compared to the Day	Gerence in proportions of patients with conversion of tive RT-PCR to negative RT-PCR as assessed at Day 1, 8, Day 14 and Day 28
	inges in chest imaging from Screening (Day 0)to Day 5 or 14 (if applicable) as defined by:
0]	Number of quadrants/ pulmonary lobes affected

CONFIDENTIAL Page 23 of 66

	 Change in number and/or size of COVID-19 pulmonary lesions (ground-glass opacity, consolidation, mix pattern) assessed by chest CT/X-ray
To evaluate the Clinical Benefit of Silmitasertib (CX-4945) relative to the control arm in patients with Severe COVID-19.	 Days of hospitalization from randomization through Day 28. Days of supplemental oxygen (if applicable) from randomization through Day 28. All-cause mortality status: the number of deaths occurred in each treatment group from randomization through Day 60. Days of non-invasive ventilation/high flow oxygen (if applicable) from randomization through Day 28. Days of invasive mechanical ventilation/ECMO (if applicable) from randomization through Day 28. Number of patients returned to room air after randomization through Day 14 or Day 28. Change in pulse oxygen saturation (SpO2) from randomization to Day 4, 8, 11, 14 and 28. Number of documented venous thromboembolism (VTE), arterial thrombosis (stroke, myocardial infarction, other) and microthrombosis events from randomization through Day 28. Changes in EQ-D5-5L (used as an indicator of symptom improvement) from randomization to Day 8, 14 and 28.
To evaluate changes in inflammatory markers	 Changes in plasma IL-6 level from randomization to Day 4, 8, 11, and 14 Changes in CRP, LDH, CPK, ferritin, D-dimer from randomization to Day 4, 8, 11, and 14

CONFIDENTIAL Page 24 of 66

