8.2.2.7. Chest Radiograph or CT

Chest X-ray or chest CT will be done and evaluated locally according to the standard site practice at the time points described in the Schedule of Activities (see **Section 1.3**). Responses to CX-4945 administration will be followed on radiograph or CT scans using the Response Evaluation in COVID-19 patients with pneumonia. The chest-CT analysis will be performed considering number of pulmonary lesions, lesion's extend, number of pulmonary lobes affected, and common COVID-19 typical abnormalities like consolidation, glass-round opacity and mix pattern.

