9.3. SAMPLE SIZE DETERMINATION AND RATIONALE

A total of 40 subjects will be randomized 1:1 in this study. The sample size is based on clinical judgment. No statistical power calculation will be used to establish the sample size for this proof-of-concept study.

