9.5. BLINDING

This is an open label study.

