9.7.3. Missing Data

CONFIDENTIAL Page 50 of 66

The method for handling missing data will be included in the statistical analysis plan. Every effort will be made to obtain required data at each scheduled evaluation from all subjects who have been randomized in the study to minimize missing data. However, in the event when there is missing data the following imputation methods will be used.

For activity/efficacy evaluations, multiple imputation methods will be used to handle missing data and will be detailed in the Statistical analysis Plan (SAP). This imputation method is a robust method to impute potential missing measurements.

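### Chest-imaging change serves a between-arm anti-viral objective, but follow-up scans depend on an unblinded clinical decision, so an arm comparison is open to selection bias of unknown size and direction

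*Combined protocol and SAP*

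**What the plan says.** - **Endpoint.** The Synopsis (Section 1.1) lists "Changes in chest imaging from Screening to Day 5 or 14 (if applicable) as defined by" the number of quadrants or lobes affected and the number or size of lesions on CT or X-ray. Section 3 places this under an objective that seeks "evidence of anti-viral activity of CX-4945 as compared to the" control arm.
- **Timing.** The Schedule of Activities marks imaging at Screening and then "Day 5, Day 14 if indicated [14", the bracket pointing to footnote 14. That footnote reads "Chest radiograph or CT will be performed if clinically indicated by the treating physician".
- **Reading.** Section 8.2.2.7: "Chest X-ray or chest CT will be done and evaluated locally according to the standard site practice". It refers back to the Schedule for timing, gives detailed reading criteria only for CT, and describes no central or blinded read.
- **Blinding.** Section 9.5: "This is an open label study".
- **Analysis.** Section 9.7.1.1 makes all randomized subjects the primary population for efficacy endpoints. Section 9.8.4.1 names ANCOVA or rank-ANCOVA for continuous data and logistic or proportional odds models for categorical data. Section 9.8.4 says that nothing inferential is planned.
- **Missing data.** Section 9.7.3: "For activity/efficacy evaluations, multiple imputation methods will be used to handle missing data", with detail left to the SAP. It makes no exception for imaging.

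**The concern.** Whether a patient has a follow-up image is settled after randomization, by a clinician who knows the arm and is responding to the patient's course. Discharge adds a second plausible route. It counts towards recovery (Section 8.2.2.1), and follow-up may then be by telephone, text, email or telehealth (Section 8.1.2), so early recoverers may be less likely to have a Day 14 image. Randomization protects a comparison of all 40 patients. It does not protect a comparison of those who happened to be scanned.

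Mixing modalities adds noise: without a rule that baseline and follow-up use the same technique, an apparent change in lesion number or size may reflect the technique.

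At stake is how an early signal is read. A by-arm difference in imaging could be taken as evidence for or against anti-viral activity when part of it comes from who was scanned. Imputing the unscanned patients would make the result look complete without adding observed data.

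**Working it through.** **Inputs from the protocol.** Section 9.3: "A total of 40 subjects will be randomized 1:1 in this study", so 20 per arm. That section does no power calculation, and no imaging rate or imaging effect size is given anywhere, so there is no plan figure to reproduce. Every imaging rate below is an assumption.

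**1. Binary outcome, same imaging rule in both arms.** Assume true improvement of 60% (Arm A) and 40% (Arm B), with 20% of improvers and 80% of non-improvers imaged in either arm.
- Arm A: 0.6×0.2 / (0.6×0.2 + 0.4×0.8) = 0.12/0.44 = 27.3%, from 20×0.44 = 8.8 imaged patients.
- Arm B: 0.4×0.2 / (0.4×0.2 + 0.6×0.8) = 0.08/0.56 = 14.3%, from 20×0.56 = 11.2 imaged patients.
- Risk difference: 20 points true, 13 observed.
- Odds ratio: true (0.6/0.4)/(0.4/0.6) = 2.25; observed (0.12/0.32)/(0.08/0.48) = 2.25.

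In general, observed odds ratio = true odds ratio × (improver-to-non-improver imaging ratio in A) / (the same ratio in B). An identical rule makes that factor 1. The risk difference is distorted here; the odds ratio is not.

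**2. Mean change.** Simulation of 2,000,000 patients per scenario: change score with SD 1 (positive = worse) and P(imaged) = logistic(slope × change + shift × Arm A). Entries are the unadjusted A minus B difference in means among imaged patients.

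| True effect | Arm shift | Slope 0 | Slope 1 | Slope 2 |
|---|---|---|---|---|
| 0 | 0 | 0.00 | 0.00 | 0.00 |
| 0 | -1 (A imaged less readily) | 0.00 | +0.17 | +0.19 |
| 0 | +1 (A imaged more readily) | 0.00 | -0.16 | -0.17 |
| -0.5 | 0 | -0.50 | -0.41 | -0.31 |
| -0.5 | -1 | -0.50 | -0.24 | -0.11 |
| -0.5 | +1 | -0.50 | -0.58 | -0.50 |

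With slope 0, imaging is unrelated to outcome and there is no bias. With an identical rule and no true effect there is again none. With an identical rule and a true effect, the effect shrinks, because fewer treated patients meet the indication (40% or 35% imaged, against 50% in control). With different thresholds, the bias goes either way or happens to cancel.

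**3. Precision.** The 95% half-width is 1.96×√(2/n) SD for n imaged per arm: 0.62 (n = 20), 0.72 (n = 15), 0.88 (n = 10), 1.13 (n = 6).

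**4. What the unscanned patients could hide.** If a share f of each arm is imaged and equal proportions of those improve, the difference over all randomized patients can lie anywhere within ±(1 − f): ±25 points at 75%, ±50 at 50%, ±70 at 30%. Narrowing this takes an assumption about patients not scanned.

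**The case against.** The strongest case on the other side has five parts.

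- **The comparison may not be planned.** Section 9.8.4 disclaims inference, and the endpoint is worded as change, not as a difference between arms. But the objective is comparative and Section 9.8.4.1 names between-arm models. By-arm summaries of a selected subset also carry the same selection. The two sections conflict, and the objection only partly stands.
- **The endpoint applies only where a scan exists.** That is a fair reading of its qualifier. Section 9.7.3 also speaks of required data at scheduled evaluations, so a scan never indicated may not count as missing. A reader might infer that the plan will impute such scans as if their absence were unrelated to the result. The documents do not say so; they leave it open.
- **Imputation could help.** The daily ordinal scale, SpO2 and laboratory values might explain much of the indication. That is possible, but no such model is specified, at most 20 patients per arm would support it, and an unblinded indication makes dependence on the unseen result plausible.
- **Day 5 may be fixed.** The schedule entry can be read as making only Day 14 conditional. Footnote 14 and the endpoint wording point the other way, and Day 5 has no visit column. This needs clarifying.
- **Imprecision dominates.** This stands. A bias of 0.16 to 0.19 SD is small beside a half-width of at least 0.62 SD.

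A reader might also infer that worsening patients are scanned and recovering ones are not, or that a false benefit will appear. If improvers were imaged 40% of the time in Arm A and 20% in Arm B, with non-improvers at 80% in both, a true 50% vs 50% would show as 0.20/0.60 = 33% vs 0.10/0.50 = 20%. Swapping the arms gives the opposite. Both need an assumed arm-by-outcome difference in imaging that no section supports.

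**Conclusion.** The concern holds in a limited form. The protocol attaches a between-arm anti-viral objective to scans obtained at an unblinded clinician's discretion, and it has no rule for patients not scanned and none for modality. A contrast built on those scans is open to selection bias.

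It would go too far to say that the comparison cannot be unbiased. It is unbiased if imaging is unrelated to outcome, and under an identical rule it is unbiased when there is no effect. Nothing in the design secures either condition.

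The figures in the working depend wholly on assumed imaging rates and show what could happen, not what will. This is one secondary endpoint in an unpowered proof-of-concept trial with a safety primary endpoint, so the priority is low to moderate.

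**What to change.** Change the wording of Section 3 (and the matching Synopsis text) and the SAP:

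1. Make the imaging endpoint descriptive only, with no between-arm model and no claim of anti-viral activity drawn from it.
2. State that scans not clinically indicated are not multiply imputed. This belongs with item 1: dropping imputation while keeping the comparison would leave a complete-case contrast that could be more biased.
3. Report, by arm and time point, how many patients were imaged and why.
4. Summarise change only in same-modality pairs (CT with CT, X-ray with X-ray).
5. Clarify whether Day 5 imaging is conditional.
6. Reconcile Section 9.8.4 with Section 9.8.4.1 on whether arms are compared inferentially.

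The cost is wording, plus a recorded reason for each scan if none is collected now. No extra scans and no change in care are involved. Section 9.8 has the SAP approved before database lock, which leaves room for the SAP items. The downside is giving up one exploratory comparison that is already imprecise at 20 per arm. This is a cheap improvement.

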3. OBJECTIVES AND ENDPOINTS

Primary Objective	Primary Endpoint
To assess safety and tolerability of CX-4945 administered orally twice daily to patients with severe COVID-19	• Adverse Events experienced by patients from randomization to Day 60 (including vital signs, physical findings, clinical laboratory, and ECG results) as characterized by type, frequency, severity (as graded by Common Terminology Criteria for Adverse Events (CTCAE version 5.0), timing, seriousness, and relationship to study therapy.
Secondary Objectives	Secondary Endpoints
• To compare time to clinical recovery in the CX-4945 treatment group evaluated from randomization through Day 28 as compared to the control arm.	• Number of days from randomization to discharge, or alleviation of cough (defined as mild or absent in a patient reported scale of 0=absent, 1=mild, 2=moderate, and 3=severe). Improvement must be sustained for at least 48 hours.
	• Number of days from randomization to normalization of fever (defined as <36.6°C from axillary site, or < 37.2°C from oral site or < 37.8°C from rectal or tympanic site), normalization of respiratory rate (< 24 bpm while breathing room air), resolution of hypoxia (defined as SpO2 ≥ 93% in room air or P/F ≥ 300 mmHg). All these improvements must be sustained for at least 48 hours.
	 Number of days from randomization to the first day on which the subject satisfies one of the following three categories from the ordinal NIAID 8-point Clinical Progression Outcomes scale collected daily from randomization through Day 28:
	Hospitalized, not requiring supplemental oxygen - no longer requires ongoing medical care;
	 Not hospitalized, limitation on activities and/or requiring home oxygen;
	Not hospitalized, no limitations on activities.
To compare changes in clinical status of patients enrolled to CX-4945 treatment arm as	Difference in percentage of subjects with clinical recovery compared at Day 14 and Day 28. Clinical recovery is defined as:

CONFIDENTIAL Page 22 of 66

s. ty	ite, or < 37.2°C from oral site or < 37.8°C from rectal or ympanic site), normalization of respiratory rate (< 24 bpm
a	while breathing room air), resolution of hypoxia (defined as $SpO2 \ge 93\%$ in room air or $P/F \ge 300$ mmHg). All these mprovements must be sustained for at least 48 hours.
Day	centage of participants at each clinical status at Day 14 and 28 assessed by using the ordinal NIAID 8- point Clinical gression Outcomes scale:
1) L	Death;

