6.1.2. Randomization

Randomized treatment assignments for the subjects will be done after confirmation of subject's eligibility, and prior to any other Day 1 study assessments. Subjects will be allocated randomly into Arm A and Arm B in a 1:1 ratio.

Arm SOC/ Daily dose of Dose AM Dose PM Dose No. of **SUPPORTIVE** CX-4945 administration capsules/day (mg) (mg) **CARE** (mg) b.i.d. (mg) 1000 1000 Assigned by the 2000 1000 10 A investigator 0 0 0 0 0 В Assigned by the investigator

Table 2. Method of Assignment to Treatment

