8.1. STUDY PROCEDURES

8.1.1. Screening Period:

The subject will sign and date the informed consent form (ICF) and Health Insurance Portability Accountability Act (HIPAA) authorization (according to site policy and practices) prior to any study-related procedures. The study center will maintain the study-specific screening and enrollment logs at their site.

For screening procedures see the Schedule of Activities in Section 1.3 and Assessments in Section 8.2.

8.1.2. Treatment Period:

For the treatment period procedures see the Schedule of Activities in Section 1.3 and Assessments in Section 8.2.

Subjects who meet the eligibility criteria will be randomized prior to any other Day 1 study procedures. The following evaluations and assessments should be performed on Day 1prior to treatment: review of any changes in medication history, physical examination, vital signs, clinical status – ordinal scale assessment, EQ-D5-5L questionnaire, pulse oxygen saturation (SpO2), PT-PCR, laboratory sample collection for routine serum biochemical, hematologic, coagulation, and IL6 levels analysis.

Patient follow-up should continue after discharge via approaches available to the site staff (e.g., telehealth visits, COVID-19 outpatient clinic, telephone calls, texts, and emails to the patient and close contacts). These efforts should prevent missing data while limiting additional public health risks and unnecessary community exposure.

During the treatment phase, subjects randomized to the treatment arm A will receive CX-4945 (1000 mg) twice a day for up to 14 days. Details on study drug administration can be found in **Section 6**.

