8.2.2. Efficacy/Anti-viral Activity Assessment

8.2.2.1. Clinical Evaluation to Assess Recovery

CONFIDENTIAL Page 41 of 66

Assessment of recovery at the time points described in the Schedule of Activities (see **Section 1.3**) is based on hospital discharge or normalization of fever, respiratory rate, alleviation of cough, and resolution of hypoxia. Normalization of fever (defined as $<36.6^{\circ}$ C from axillary site, or $<37.2^{\circ}$ C from oral site or $<37.8^{\circ}$ C from rectal or tympanic site), respiratory rate (<24 bpm while breathing room air), alleviation of cough (defined as mild or absent in a patient reported scale of 0=absent, 1=mild, 2=moderate, and 3=severe) and resolution of hypoxia (defined as SpO2 \ge 93% in room air or P/F \ge 300 mmHg) must be sustained for at least 48 hours.

8.2.2.2. **EQ-D5-5L**

Administration of questionnaires for patient-reported outcomes at the time points described in the Schedule of Activities. The 5-level EQ-5D version (EQ-5D-5L) will be used to assess five dimensions: mobility, self-care, usual activities, pain/discomfort and anxiety/depression.

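### Allocation precedes the Day 1 assessments in an open-label trial, so the only EQ-5D-5L baseline is a self-report made once the arm can be known

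*Combined protocol and SAP*

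**What the plan says.** Three places set the order of events on Day 1, and they agree.

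- Schedule of Activities (Section 1.3), footnote 15: "Patient number and treatment arm allocation is performed on Day 1, prior to any Day 1 study assessments".
- Section 6.1.2 places random assignment after eligibility is confirmed and "prior to any other Day 1 study assessments".
- Section 8.1.2: "Subjects who meet the eligibility criteria will be randomized prior to any other Day 1 study procedures". It then gives a list that includes the EQ-5D-5L, introduced by: "The following evaluations and assessments should be performed on Day 1prior to treatment".

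Section 9.5 states: "This is an open label study". In Table 1 the EQ-5D-5L is due on Days 1, 8, 14 and 28, with no screening entry, and Day 1 is labelled the baseline. The secondary endpoint in the Synopsis and Section 3 is "Changes in EQ-D5-5L (used as an indicator of symptom improvement) from randomization to Day 8, 14 and 28". Section 8.2.2.2 treats the instrument as patient-reported: "The 5-level EQ-5D version (EQ-5D-5L) will be used to assess five dimensions". It does not say which score is the endpoint.

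Cough severity is also self-reported. It enters the Section 3 recovery endpoint "Number of days from randomization to discharge, or alleviation of cough", where improvement must last 48 hours. Table 1 schedules the recovery assessment from Day 1, but the pre-treatment list in Section 8.1.2 omits it.

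**The concern.** A baseline completed before allocation differs between arms only by chance. One completed afterwards can also reflect what the patient thinks of the arm received. A patient disappointed to be on standard care alone, or encouraged to be on the new drug, may rate the same health differently. The present rule keeps the Day 1 questionnaire clear of the drug, because it precedes dosing, but not of knowledge of the arm. Nothing in the document withholds the arm until the form is complete.

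Vital signs, SpO2, the routine laboratory panels and the ordinal scale also have a screening value. IL-6 does not, but it is a laboratory measure. Among the change-from-randomization endpoints, the EQ-5D-5L is the self-report left without any value from before allocation.

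Cough is affected less. It is a threshold with no baseline subtracted, so its Day 1 grade only shows who already has mild or absent cough at time zero. Because cough is one of several qualifying symptoms in inclusion criterion 3, some patients may be in that state whatever the order.

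**Working it through.** The plan gives no figure to reproduce. Section 9.3 sets 40 patients, randomized 1:1, on clinical judgment, with no SD, effect size, alpha or power. The shifts and slopes below are therefore assumptions. Units are SDs of whichever EQ-5D-5L score is used, with a higher score meaning better health.

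**Bias.** Let d1 be the reporting shift in one arm on Day 1, d2 the shift at a later visit, and b the slope of the later score on baseline (0.3 to 0.7 assumed).

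- Change score, current order: bias = d2 − d1.
- Baseline-adjusted ANCOVA, current order: bias = d2 − b × d1.
- Questionnaire before allocation: d1 = 0, so both equal d2.

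| Assumed shifts | Change score now | ANCOVA now | Either, after reordering |
|---|---|---|---|
| d1 = 0.2, d2 = 0 | −0.2 | −0.06 to −0.14 | 0 |
| d1 = 0.5, d2 = 0 | −0.5 | −0.15 to −0.35 | 0 |
| d1 = 0.2, d2 = 0.2 | 0 | 0.06 to 0.14 | 0.2 |
| d1 = −0.2, d2 = 0.2 | 0.4 | 0.26 to 0.34 | 0.2 |

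A simulation of 6,000 trials with 20 per arm and b = 0.5 agrees with the formulas to within 0.01.

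For d2 > 0, reordering lowers the absolute change-score bias only if d1 < 0 or d1 > 2 × d2. It lowers the absolute ANCOVA bias only if d1 < 0 or d1 > 2 × d2 / b.

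**Effect on a test, if one is done.** Take b = 0.5, d1 = 0.2, d2 = 0 and equal SDs, so that b is also the correlation.

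- Change score: SE = √(2 × 0.5) × √(2/20) = 0.316, and bias/SE = 0.2/0.316 = 0.63. The nominal 5% two-sided error becomes 9.7%.
- ANCOVA: SE = √(1 − 0.25) × √(2/20) = 0.274, and bias/SE = 0.10/0.274 = 0.37. The error becomes 6.5%.

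**Could the trial detect a shift afterwards?** The SE of the baseline difference is √(2/20) = 0.316 SD. Chance alone therefore spans ±1.96 × 0.316 = ±0.62 SD (95%). For a two-sided 5% t-test with 38 degrees of freedom:

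- power is 9.5% for a 0.2 SD shift (noncentrality 0.2/0.316 = 0.63);
- power is 34% for a 0.5 SD shift (noncentrality 0.5/0.316 = 1.58);
- 80% power needs a shift of 0.91 SD.

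**The case against.** The strongest reply is that the change is not shown to reduce bias. Post-baseline answers stay unblinded in either order. If patients shift their reports equally at every visit, the current order cancels the shift in a change score and partly cancels it in ANCOVA; moving the questionnaire would raise the bias from 0, or from 0.06 to 0.14, to 0.2 SD. This is right, and the benefit should not be sold as a guaranteed reduction. It is not a reason to keep the order. Cancellation depends on two unknown shifts having the same sign and similar size, and the plan does not give it as a reason for the order. A clean baseline leaves one unknown instead of two.

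A second reply is that the harm is conditional, since no section says the patient learns the arm before filling in the form. That also stands: knowledge is possible, not certain. But nothing prevents it.

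Third, the SD-scale figures may not fit the eventual analysis. The five dimensions are ordinal, Appendix 1 also contains a 0 to 100 scale, Section 9.7.2 leaves covariates to a separate SAP, and Section 9.8.4 plans no inferential statistics while Section 9.8.4.1 names ANCOVA. The figures are therefore illustrative. The argument about order does not depend on the score chosen, and if only descriptive change scores are shown, d1 enters in full.

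Last, the reach is small: one secondary endpoint among many, with cough affected only at the margin, in an exploratory trial with a safety primary endpoint. This is why the point is rated minor.

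**Conclusion.** The concern holds, as a minor point. On the document's own text, the only EQ-5D-5L baseline is a self-report taken after allocation in an unblinded trial. This rests on reading footnote 15, Sections 6.1.2, 8.1.2 and 9.5, and Table 1 together, and confidence in that reading is high. The size of any resulting bias is unknown, and a shift of plausible size could not be told from chance imbalance with 20 per arm. The gain from reordering is a baseline independent of the arm; total bias could move either way. The primary safety endpoint is not affected.

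**What to change.** Change the order in footnote 15, Section 6.1.2 and Section 8.1.2, for example: *Allocation is made on Day 1 after consent and confirmation of eligibility, and after the Day 1 EQ-5D-5L and cough/recovery assessment are completed; dosing follows allocation.* The form can carry the subject identifier which, on the reading of Section 5.2, exists from screening. In addition:

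- Add the cough/recovery assessment to the pre-treatment list in Section 8.1.2.
- Record the clock times of the EQ-5D-5L and of allocation.
- If a patient cannot complete the form, document the reason, as Section 8.2 already requires, and proceed to allocation.
- In the SAP, show EQ-5D-5L values by visit beside the change scores, and state that post-baseline reports are unblinded.

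A related timing also needs reconciling. Section 6.3.1 expects Arm A patients who choose the antiemetic patch to apply it about 24 hours before Day 1, yet the arm is assigned on Day 1. The section has an oral fallback, but the two timings do not fit together.

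The cost is a slightly later allocation on Day 1 and the noting of clock times. No assessment is added: both are already scheduled on Day 1, the EQ-5D-5L is already due before treatment, and consent is taken at screening. Eligibility and sample size do not change.
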